3 STATISTICAL METHODS

3.1 General Considerations

In general, unless specified otherwise, baseline is defined as the last non-missing assessment prior to dosing. If the baseline is missing following the above definition, baseline evaluations will not be imputed and will be considered as missing. All safety analyses will be performed on the As-treated population. All PK analyses will be conducted using the PK-population. Immunogenicity evaluation will be based on the As-treated population. All other analyses will be performed on the ITT population unless stated otherwise. All data will be provided in data listings sorted by treatment group and subject number. The placebo CCI groups will be pooled for planned analyses, except where stated otherwise. All tabular summaries will be presented by treatment group. Categorical data will be summarized by the number and percentage of subjects in each category. Continuous variables will be summarized by descriptive statistics including number of subjects, mean, standard deviation (SD), median, minimum, and maximum. All statistical tests will be two-sided at an alpha = 0.1 significance level unless stated otherwise.

Day 1 is the first dosing date. Prior to Day 1, study days will be calculated as (sample collection date – Day 1). After Day 1, study days will be calculated as (sample collection date – Day 1 + 1).

3.1.1 General Computation Rules

3.1.1.1 Absolute and Percent Change from Baseline

Absolute change from baseline will be computed as (visit value – baseline value). Percent change from baseline will be computed as (visit value – baseline value)*100/baseline value.

If either a visit value or the baseline value is missing, then the absolute change from baseline value and the percent change from baseline will also be set to missing. If a visit value is non-zero while the baseline value is zero, then the absolute change from baseline will be computed but the percent change from baseline will be set to missing. If a visit value is zero and the baseline value is zero, the percent change will also be zero.

3.1.2 Visit Windows

Visit windows will be used for all scheduled assessments to allow for by-visit analyses, since not all assessments are performed on the scheduled day. The analysis visit windows will be calculated by bisecting the scheduled visit days. The lower limit of each window will be the mean of the two adjacent planned study days, rounded up to the nearest integer. The upper

limit of each window will be the mean of the two adjacent planned study days, rounded down to the nearest integer.

The visit result will be missing if no assessment was reported within the specified visit window around the scheduled date. If multiple readings are recorded within a single visit window, then rules will be applied, as follows:

- If there are 2 or more observations within the same visit window, the non-missing observation closest to the scheduled visit will be used in the analysis.
- If 2 observations are equidistant from the scheduled visit, the non-missing observation with the earlier collection date or time will be used in the analysis.
- If two observations are collected on the same date, the non-missing observation with the earlier collection time will be used in the analysis.
- Additional rules for cases not covered by the 2 rules above will be documented in the Analysis Conventions Document.

For EASI, IGA and SCORAD, adjusted protocol-defined visit windows will be used as defined in

[Table 1.](#)

Table 1 Adjusted Protocol-defined Visit Windows for EASI, IGA, and SCORAD

Visit Number	Name/Week Number	Scheduled Study Day in the Protocol	Visit Windows
1	Screening ^a	-28 to -12	Study Day \leq -12
2	TCS/TCI Wash Out ^a	-11 to -8	-11 \leq Study Day \leq -8
3	Week 0 (Day 1) ^a	1	-7 \leq Study Day \leq 1
5	Week 1	8	2 \leq Study Day \leq 11
6	Week 2	15	12 \leq Study Day \leq 22
7	Week 4	29	23 \leq Study Day \leq 43
8	Week 8	57	44 \leq Study Day \leq 71
9	Week 12	85	72 \leq Study Day \leq 99
10	Week 16	113	100 \leq Study Day \leq 127
11	Week 20	141	128 \leq Study Day \leq 155
12	Week 24	169	Study Day \geq 156

^a The Screening and Week 0 (Day 1) visit windows are applicable only when the visit is present for descriptive statistics in the summary tables for EASI, IGA, and SCORAD. For analyses, baseline is defined as the last assessment value prior to dosing unless stated otherwise.

For the patient-reported questionnaires collected by electronic PRO, the data will be summarized based on the visit windows provided (Table 2).

Table 2 Visit Windows for PRO Data

Questionnaire	Collection Frequency and Scheduled Visits	Visit Windows
Pruritus NRS	
 Daily 	Not Applicable
Skin pain NRS	
 Daily 	Not Applicable
Moisturizer use	
 Daily 	Not Applicable
5-D Pruritus Scale	
 Initial assessment at site: Day 1 At site: Weeks 2, 4, 8, 12, 16, 20 and 24 	Day 1: Study Day ≤ 1 Week 2: $2 \leq$ Study Day ≤ 22 Week 4: $23 \leq$ Study Day ≤ 43 Week 8: $44 \leq$ Study Day ≤ 71 Week 12: $72 \leq$ Study Day ≤ 99 Week 16: $100 \leq$ Study Day ≤ 128 Week 20: $128 \leq$ Study Day ≤ 155 Week 24: Study Day ≥ 156
DLQI	
 Initial assessment at site: Day 1 At site: Weeks 2, 4, 8, 12, 16, 20 and 24 	Same as 5-D Pruritus Scale
PGI-S	
 Initial assessment at site: Day 1 At site: Weeks 2, 4, 8, 12, 16, 20 and 24 	Same as 5-D Pruritus Scale
POEM	
 Initial assessment at site: Day 1 At site: Weeks 2, 4, 8, 12, 16, 20 and 24 	Same as 5-D Pruritus Scale
ACQ	
 Initial assessment at site: Day 1 At site: Weeks 4, 8, 12, 16 and 24 	Day 1: Study Day ≤ 1 Week 4: $2 \leq$ Study Day ≤ 43 Week 8: $44 \leq$ Study Day ≤ 71 Week 12: $72 \leq$ Study Day ≤ 99 Week 16: $100 \leq$ Study Day ≤ 141 Week 24: Study Day ≥ 142
SNOT-22	
 Initial assessment at site: Day 1 At site: Weeks 4, 8, 12, 16 and 24 	Same as ACQ

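### SAP Table 2 puts Day 128 in both the Week 16 and Week 20 windows for four questionnaires, and the bisecting rule in SAP 3.1.2 shares midpoint days between visits for assessments with no printed table

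*SAP*

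**What the plan says.** SAP 3.1.2 sets one method for the whole study: "Visit windows will be used for all scheduled assessments to allow for by-visit analyses". Windows are formed by bisecting the planned days. For the start, "The lower limit of each window will be the mean of the two adjacent planned study days, rounded up to the nearest integer". For the end, the "limit of each window will be the mean of the two adjacent planned study days, rounded down to the nearest integer".

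Two tables then print explicit limits. Table 1 covers EASI, IGA and SCORAD and gives Week 16 as Days 100 to 127 and Week 20 as Days 128 to 155. Table 2 covers the questionnaires. For 5-D itch it opens Week 16 at Day 100 and closes it at "Study Day ≤ 128", then opens Week 20 at Day 128. DLQI, PGI-S and POEM are assigned the 5-D windows. ACQ and SNOT-22 have their own windows, with Week 16 ending at Day 141 and Week 24 starting at Day 142. Daily pruritus and skin pain NRS have no windows.

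The selection rules in the same section apply when several readings fall in one window: the nearest usable one is taken, and the earlier one if two are equally near. No rule covers one reading that falls in two windows. Laboratory tests, vital signs, ECG and blood biomarkers have no printed table.

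**The concern.** A visit-window scheme should place each record at one visit. Here it does not, in two places.

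In Table 2, Day 128 belongs to both Week 16 and Week 20. All four instruments are secondary endpoints at Week 16. EASI is scheduled alongside them at both weeks, so a subject seen on Day 128 would have EASI counted at Week 20 while the DLQI from the same visit qualifies for both weeks.

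In the general rule, a whole-number midpoint is unchanged by rounding up or down. The same day then closes one window and opens the next, and this governs every assessment that lacks a table.

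At stake is reproducibility more than bias. Two programmers following the text could build different analysis datasets, and an off-schedule or early-discontinuation record could appear at two visits or at the farther one.

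**Working it through.** **Inputs.** Planned days come from the SAP Table 1 column headed "Scheduled Study Day in the Protocol": 1, 8, 15, 29, 57, 85, 113, 141, 169. Schedules for the other assessments come from Protocol Tables 7 and 8.

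**Formula.** Lower limit = ceil((previous day + this day)/2). Upper limit = floor((this day + next day)/2).

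**Rule against the printed tables:**

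| Visit pair | Midpoint | Rule: earlier ends / later starts | Table 1 | Table 2, 5-D |
|---|---|---|---|---|
| Week 1 / 2 | (8+15)/2 = 11.5 | 11 / 12 | 11 / 12 | no Week 1 visit |
| Week 2 / 4 | (15+29)/2 = 22 | 22 / 22 | 22 / 23 | 22 / 23 |
| Week 4 / 8 | (29+57)/2 = 43 | 43 / 43 | 43 / 44 | 43 / 44 |
| Week 8 / 12 | (57+85)/2 = 71 | 71 / 71 | 71 / 72 | 71 / 72 |
| Week 12 / 16 | (85+113)/2 = 99 | 99 / 99 | 99 / 100 | 99 / 100 |
| Week 16 / 20 | (113+141)/2 = 127 | 127 / 127 | 127 / 128 | **128 / 128** |
| Week 20 / 24 | (141+169)/2 = 155 | 155 / 155 | 155 / 156 | 155 / 156 |

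Every post-baseline upper limit in both tables matches the rule except the 128. Every later window in these rows starts the day after the midpoint, which gives the midpoint day to the earlier visit. ACQ and SNOT-22 follow the same convention: (113+169)/2 = 141, printed as 141/142.

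**When a Day 128 record is used.**
- Distance to Week 16: 128 − 113 = 15 days. Any usable record in Days 100 to 127 is at most 14 days from Day 113 and displaces it.
- Distance to Week 20: 141 − 128 = 13 days. Any usable record in Days 129 to 153 is at most 12 days from Day 141 and displaces it. A Day 154 record is also 13 days away, and the earlier-date rule then keeps Day 128.
- Use at Week 16 therefore needs no usable record in Days 100 to 127. Use at both visits also needs none in Days 129 to 153.

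**Where it would enter.** The Week 16 MMRMs for 5-D, POEM and DLQI (SAP 3.4.2.3) use data up to Week 16, so the record enters once, as Week 16. The longer MMRMs (SAP 3.4.3.11 to 3.4.3.13) and the by-visit summaries include Weeks 16 and 20, so it can enter twice. PGI-S is summarized descriptively only.

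**Shared days under the rule where no table is printed:**
- Chemistry and hematology follow the full schedule: 22, 43, 71, 99, 127, 155, so six.
- Vital signs have no Week 20 visit, so the last midpoint is (113+169)/2 = 141. Shared days are 22, 43, 71, 99, 141, so five.
- ECG has neither Week 2 nor Week 20. (8+29)/2 = 18.5 gives no tie. Shared days are 43, 71, 99, 141, so four.
- Biomarkers vary with their own schedules.

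**Check of the correction.** With Week 16 ending at Day 127, the 5-D windows have no overlapping and no uncovered days. Setting the lower limit to floor(midpoint) + 1 gives 23, 44, 72, 100, 128 and 156, and 142 for ACQ at Week 24, which are the lower limits already printed from Week 4 onward.

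**The case against.** The best reply is that the intended convention is plain. Both tables resolve every other tie by giving the midpoint day to the earlier visit, so 128 reads as a one-digit slip affecting one day and one visit pair. The nearest-record rule removes the shared record in the ordinary case, because double use requires that neither visit has a closer record. This stands, and it is why the point is minor.

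A reader might infer that the secondary questionnaire endpoints are double-counted. The documents do not support that: the Week 16 models stop at Week 16, and Week 20 results are exploratory. A reader might also carry the six shared days over to all untabulated data, or turn them into a share of follow-up days. The count differs by schedule, and a share of calendar days is not a share of records.

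It can also be said that the matter is partly covered elsewhere. SAP 3.7 assigns early-discontinuation ADA samples to a single nominal visit, but only ADA. SAP 3.1.2 defers further cases to an Analysis Conventions Document, but under the heading of several readings in one window. Neither settles one record that qualifies for two windows.

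**Conclusion.** The point holds as a minor correction. The Day 128 limit is wrong by the SAP's own rule and by Table 1, and the rule as worded does not give one visit per record when the midpoint is a whole number.

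The questionnaire problem is confined to records on exactly Day 128 for 5-D itch, DLQI, PGI-S and POEM, with no closer Week 16 record. In the Week 16 MMRMs the consequence is assignment to the farther visit. Duplication is possible only in by-visit summaries and the Week 24 models, and only if Week 20 also lacks a closer record. The rule's ties concern laboratory, vital sign, ECG and some biomarker data. The primary endpoint, EASI responders, IGA, SCORAD, ACQ-6 and SNOT-22 use printed windows that do not overlap.

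The view that the numerical effect is very small assumes that most visits fall near their planned days. The documents give no distribution of actual visit dates, so the number of affected records cannot be computed.

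**What to change.** In SAP Table 2, end the Week 16 window for 5-D itch at Day 127; DLQI, PGI-S and POEM follow automatically. In SAP 3.1.2, state that each window starts the day after the previous one ends, so that a whole-number midpoint belongs to the earlier visit, and that each record is assigned to one visit only. This matches the convention the tables otherwise follow. The cost is one number and one sentence, with no change to design, data collection or models.

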3.2 Analysis Populations

There are 3 analysis populations defined for this study (Table 3). A summary of the analysis populations by treatment group will be provided.

Table 3 Analysis Populations

Population	Description
ITT	Subjects who are randomized and receive any investigational product. Subjects will be analyzed according to their randomized treatment group.
As-treated	Subjects who are randomized and receive any investigational product. Subjects will be analyzed according to the treatment they actually receive.

Table 3 Analysis Populations

Population	Description
PK	Subjects who receive at least 1 dose of MEDI3506 and have at least 1 detectable serum concentration measurement post first dose of treatment. Subjects will be analyzed according to the treatment they actually receive.

ITT = intent-to-treat; PK = pharmacokinetic(s).

3.3 Study Subjects

3.3.1 Subject Disposition and Completion Status

Summaries of subject eligibility, randomization, treatment received, and subjects randomized but not treated will be provided. In addition, subject disposition throughout the study and by visit with respect to treatment completion and follow-up completion will be provided. The summaries will be presented by treatment group and for all subjects combined. The denominators for this summary will include all subjects who were randomized into the study.

The number and percentage of subjects with one or more disruptions due to COVID-19 pandemic will be presented by treatment group. A listing of all subjects affected by the COVID-19 related study disruption by unique subject number identifier and by investigational site, and a description of how the individual's participation was altered, will be produced. COVID-19 related study disruptions can be:

1. Visit related (if visit is impacted by global/country situation, then contact mode will be specified);
2. Study drug related (if study drug action taken (except "Drug Withdrawn") was impacted by global/country situation; study drug administration or location was impacted by global/country situation; who performed a study drug administration);
3. Concomitant medication related (if when treatment was stopped due to any global/country related situations ie: epidemic/pandemic, healthcare crisis etc.);
4. Discontinuation of study drug due to COVID-19 pandemic (if study drug action taken "Drug Withdrawn" was impacted by global/country situation);
5. Withdrawal from study (if primary reason for ending study is related to global/country situation).

3.3.2 Important Protocol Deviations

Important protocol deviations (IPDs) are a subset of protocol deviations that may significantly impact the completeness, accuracy, and/or reliability of the study data or that may significantly affect a subject's rights, safety, or wellbeing (ICH E3 guidance). The category of IPDs for the study are:

1. Did not fulfil eligibility criteria
2. Developed discontinuation criteria but continued
3. Received incorrect investigational treatment/dose
4. Received prohibited concomitant medication
5. Protocol-required procedure not adhered to
6. Other reason

Details of the definition of IPDs will be provided in the protocol deviation plan (PDP), which will be developed for the study. The method for identifying IPDs will be documented in the PDP. The list of identified IPDs will be reviewed by the study statistician, medical monitor, study physician, lead data manager and study manager. All blinded IPDs will be agreed prior to study unblinding by blinded study personnel. The review will take place at the time of primary analysis and final analysis for the study. Unblinding IPDs (ie. those that relate to study medication/dosing and which could potentially unblind a reviewer to subject's treatment group) will be agreed by unblinded personnel. The finalized list of IPDs will be approved by the study statistician, medical monitor and study physician.

The number and percentage of subjects with at least one IPD, including and excluding COVID-19 related IPDs, will be summarized following the IPD categories for each study intervention group and overall. A listing of all identified IPDs will also be provided. All issues reported due to COVID-19 pandemic, regardless of whether the type of issue is considered an IPD or not, will be listed separately.

3.3.3 Demographics and Baseline Characteristics

Demographic information related to sex, age, race, weight, height, and body mass index (BMI) will be presented by treatment group and for all subjects combined. A summary of baseline disease characteristics will include, but will not be limited to:

1. Stratification factor – Total immunoglobulin (Ig)E (< 150kU/L vs ≥ 150 kU/L)
2. Total serum IgE level (kU/L)
3. EASI score
4. EASI Score (≤ 25 points vs > 25 points)
5. Body surface area affected by AD (%)
6. Investigator’s Global Assessment (IGA) score
7. SCORAD
8. DLQI
9. 5-D itch
10. PGI-S
11. POEM
12. Peripheral blood eosinophil count (cells/μL)
13. Peripheral blood eosinophil count (cells/μL) (<300 vs ≥ 300)
14. Plasma EDN level (ng/mL)
15. *Staphylococcus aureus* (< median vs ≥ median) (lesional and non-lesional skin separately) (at final analysis only)
16. TCS use at Screening (Low Potency TCS vs Medium to High Potency TCS vs No TCS)
17. Systemic therapy use in past 6 months (Yes vs No)
18. Topical medication use not tolerated or medically inadvisable (Yes vs No)

Medical history and AD history will be summarized by treatment group and for all subjects combined.

3.3.4 Investigational Product Exposure

Exposure to investigational product will be summarized by treatment group for the As-treated population. The summary of investigational product exposure will include descriptive statistics for the number of investigational product doses administered, total amount of investigational product exposure (in mg), and dose intensity for the entire study period. Also, total amount of investigational product administered by visit (in mg) will be summarized using descriptive statistics as well as for dose intensity. Dose intensity is defined as a percent of actual dose received versus total protocol planned dose.

3.3.5 Prior and Concomitant Medications

Prior and concomitant medications (including atopic dermatitis medications) will be coded using the WHODrug-Global-B3 Drug Dictionary. All prior and concomitant medications will be presented in a data listing. Prior medications include those medications that were stopped prior to the first dose of the investigational product. Concomitant medications exclude medications that were stopped prior to the first dose of investigational product. Summaries will be provided by preferred term and treatment group, as follows:

- Prior atopic dermatitis medications

- Prior other medications (ie. non-AD medications)
- Concomitant atopic dermatitis medications
- Concomitant other medications (ie. non-AD medications)

3.3.6 Prohibited and Rescue Concomitant Medications

If a subject receives prohibited or rescue AD therapy, which may impact their efficacy assessments, they should discontinue investigational product. Prohibited and rescue AD therapy will be identified prior to unblinding. All prohibited and rescue AD therapies identified will be reviewed and a list of medications deemed to influence the disease will be made before unblinding, the list will be approved by the medical monitor.

For the purpose of analyses, prohibited and rescue concomitant medications and therapies will be summarized. Cumulative summary of prohibited and rescue medication use by visit will also be provided. In addition, the cumulative distribution plot of the proportion of subjects receiving rescue therapy will be provided. A listing of all subjects who received prohibited rescue therapies will be provided specifying the prohibited therapy and the timing of use.

3.4 Efficacy Analyses

3.4.1 Primary Efficacy Endpoint(s) and Analyses

3.4.1.1 Primary Efficacy Endpoint(s)

The primary efficacy endpoint is the percent change from baseline to Week 16 in EASI score. The EASI is a one-dimensional scoring system, measuring only the clinical signs of AD not including the symptoms. The EASI evaluates 4 anatomic regions for severity and extent of key disease signs and focuses on the acute and chronic signs of inflammation (ie, erythema, edema, papulation, excoriation, and lichenification). The maximum score is 72, with higher values indicating more severe disease.

EASI score is calculated as described (Table 4) ([Hanifin et al, 2001](#)).

Table 4 EASI Score Calculation

Body Region	Severity	Area	Score
Head/Neck (H)	The average degree of severity of each sign (erythema [E], induration/papulation [I], excoriation [EX], and lichenification [L]) is defined on a 4-point ordinal scale with half-steps (0.5, 1.5, and 2.5): 0 = none 0.5 1 = mild 1.5 2 = moderate 2.5 3 = severe	The area is defined on a 7-point ordinal scale: 0 = no eruption 1 = < 10% 2 = 10%-29% 3 = 30%-49% 4 = 50%-69% 5 = 70%-89% 6 = 90%-100%	$(E + I + Ex + L) \times Area \times 0.1$
Upper limbs (UL)			$(E + I + Ex + L) \times Area \times 0.2$
Trunk (T)			$(E + I + Ex + L) \times Area \times 0.3$
Lower limbs (LL)			$(E + I + Ex + L) \times Area \times 0.4$
EASI Score	NA	NA	Sum of scores for H, UL, T, and LL

NA = not applicable.

3.4.1.2 Handling of Dropouts and Missing Data

If any component of EASI is missing, the calculation of the score will be set to missing. For subjects who receive prohibited or rescue concomitant medications and therapies, the data obtained after the use of this therapy will be treated as missing and excluded from the primary analysis. In addition, sensitivity analyses will be performed in which the last response value recorded on the day of, or prior to, use of prohibited concomitant medications and therapies, and prohibited rescue therapies, will be carried forward.

3.4.1.3 Primary Efficacy Analysis

EASI score will be summarized with descriptive statistics (number of subjects with a valid value, mean, standard deviation, median, minimum, and maximum) by treatment group and visit. In addition, the change from baseline will be summarized with descriptive statistics for each post-baseline visit.

To assess dose response at Week 16, percent change from baseline to Week 16 in EASI score will be analyzed using a mixed-effects model for repeated measures (MMRM) including data from visits up to Week 16. The model will include treatment group, randomization stratum (total serum IgE < 150 kU/L or ≥ 150 kU/L), visit, and treatment group by visit interaction as categorical factors, with baseline EASI score as a covariate and the baseline*visit interaction term. Visit will be a repeated factor within a subject and an unstructured variance-covariance

matrix will be used to describe the correlations between observations on a subject between visits. If the unstructured variance-covariance matrix will not fit, then an alternative such as compound symmetry or first order auto-regressive will be used. The coefficient of the treatment effects at Week 16 obtained from the MMRM will then be incorporated into an MCP-Mod ([Pinheiro et al, 2014](#)), with 4 candidate models (linear, E_{\max} , and 2 Hill- E_{\max} models) to determine the dose response profile. Details of the candidate models are provided in [Appendix 1](#). As part of the MCP-Mod model, the testing of the 4 candidate dose response models will be adjusted for multiplicity using a family-wise error rate of 0.10. If more than 1 candidate model shows a statistically significant dose response, the final model will be selected based on the Akaike Information Criteria obtained from each model.

The estimand of primary interest is the difference in mean percent change from baseline to Week 16 in EASI score between MEDI3506 and placebo in the ITT population. Data that are collected after withdrawal from the study or the use of rescue therapy will be treated as missing and excluded from the analysis. Data collected from subjects who discontinue the investigational product and did not use any rescue therapy afterwards will be included in the analysis. From the final model obtained from the MCP-Mod dose response analysis, the adjusted difference in mean percent change from baseline in EASI score between the placebo group and each MEDI3506 group at Week 16 will be estimated along with the 90% confidence interval (CI) and two-sided p-value. In addition, an estimate of the adjusted difference in mean percent change from baseline in EASI at each visit for each treatment group compared to placebo arm will be summarized together with a two-sided 90% CI, and p-value.

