4.8.3 Efficacy

4.8.3.1 Primary Efficacy Analysis

Percent Change in EASI Score

The primary efficacy endpoint is the percent change from baseline to Week 16 in EASI score.

To assess dose response at Week 16, percent change from baseline to Week 16 in EASI score will be analyzed using an MMRM including data from visits up to Week 16. The model will include treatment group, randomization stratum (total serum IgE < 150 kU/L or \geq 150 kU/L), visit, and treatment group by visit interaction as categorical factors, with baseline EASI score as a covariate and the baseline*visit interaction term. Visit will be a repeated factor within a subject and an unstructured variance-covariance matrix will be used to describe the correlations between observations on a subject between visits. If the unstructured variance-covariance matrix will not fit, then suitable alternatives will be considered, with details provided in the SAP. The coefficient of the treatment effects at Week 16 obtained from the MMRM will then be incorporated into an MCP-Mod (Pinheiro et al, 2014), with 4 candidate models (linear, E_{max} , and 2 Hill- E_{max} models) to determine the dose response profile. As part of the MCP-Mod model, the testing of the 4 candidate dose response models will be adjusted for multiplicity using a family-wise error rate of 0.10. If more than 1 candidate model shows a statistically significant dose response, the final model will be selected based on the Akaike Information Criteria obtained from each model.

The estimand of primary interest is the difference in mean percent change from baseline to Week 16 in EASI score between MEDI3506 and placebo in the ITT population. Data that are collected after withdrawal from the study, or the use of rescue therapy will be treated as missing and excluded from the analysis. From the final model obtained from the MCP-Mod dose response analysis, the adjusted difference in mean percent change from baseline in EASI score between the placebo group and each MEDI3506 group at Week 16 will be estimated along with the 90% confidence interval (CI) and two-sided p-value. In addition, an estimate of the adjusted difference in mean percent change from baseline in EASI at each visit for each treatment group will be summarized together with a two-sided 90% CI, and p-value.

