2.4 Sample Size

A sample size of 144 subjects in an overall 3:1:1:3 ratio of MEDI3506 CCI : MEDI3506 CCI : MEDI3506 CCI : pooled placebo will provide at least 90% power to detect a statistically significant difference in the percent change from baseline to Week 16 in EASI score between the highest dose of MEDI3506 and pooled placebo in a responder subgroup, assuming a 35% point difference between placebo and MEDI3506 at the highest dose, based on a SD of 40% points, a two-sided 10% alpha level and 50% of subjects in the responder subgroup. Based on identical assumptions, the sample size provides > 99% power to detect a statistically significant dose response in percent change from baseline to Week 16 in EASI score in all-comers.

The calculations for dose-response assume that percent change from baseline to Week 16 in EASI score will increase monotonically with the administration of higher MEDI3506 doses. The power was calculated using a multiple comparison procedure with modelling techniques (MCP-Mod) (Bretz et al, 2005) with 4 candidate models for the dose response (linear, maximum effect attributable to the drug [E_{max}], and 2 Hill- E_{max} models). Randomization will be stratified by total IgE (< 150 kU/L or \geq 150 kU/L) at screening. The sample size calculations were performed using the R statistical computing software.

To allow for the possibility that \leq 5% of the subjects per treatment group (for MEDI3506 CCI and placebo) may be ineligible for the ITT population, the total sample size will comprise approximately 152 subjects (58 MEDI3506 CCI, 18 for MEDI3506 CCI, 18 for MEDI3506 CCI, and 58 for pooled placebo) randomized approximately to 3:1:1:3 ratio overall to the treatment groups.

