3.4.1.5 Subgroup Analyses

The consistency of the overall treatment effect on the primary endpoint will be assessed in subgroups of subjects. A MMRM, as described in Section 3.4.1.3, including data from up to Week 16, will be used for each subgroup. The analyses will be performed for subgroups, as follows:

- Total serum IgE level at baseline (< 150 kU/L vs ≥ 150 kU/L).
- Baseline IGA score (3 vs 4).
- Baseline EASI (≤ 25 points vs > 25 points).
- *S aureus* in lesional skin at baseline ($<$ median vs \geq median) (at final analysis only).
- *S aureus* in non-lesional skin at baseline ($<$ median vs \geq median) (at final analysis only).
- Age (18 to 35 years of age vs 36 to 75 years of age).
- Age at onset of AD (< 18 years of age vs ≥ 18 years of age).
- Parent having a history of AD (presence vs absence).

- Sex (male vs female).
- Race (White vs non-White).
- Region (North America vs Europe/Australia).
- Blood eosinophil count at baseline (< 300 cells/ μL vs ≥ 300 cells/ μL).
- Aeroallergens (presence vs absence).
- Food allergies (presence vs absence).
- Contact allergies (presence vs absence).
- Asthma comorbidity (presence vs absence).

The MMRM will be fitted separately to each subgroup. The analysis for each subgroup will be performed if the subgroup has at least 20% of subjects in the ITT population.

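### The only fallback covariance structures the SAP names for the MMRM assume equal variance at every visit; if one is needed and the SD rises towards Week 16, the Week 16 standard error is too small

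*SAP*

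**What the plan says.** Protocol 4.8.3.1 specifies an unstructured matrix for the primary MMRM and leaves the fallback open: "then suitable alternatives will be considered, with details provided in the SAP". SAP 3.4.1.3 fills this in: when the unstructured matrix cannot be fitted, "an alternative such as compound symmetry or first order auto-regressive will be used". It gives no order of preference, no heterogeneous-variance structure, no robust variance estimator and no degrees-of-freedom method.

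The Week 16 coefficients and their estimated covariance matrix then go into MCP-Mod (SAP Appendix 1), where the four candidate models are "adjusted for multiplicity using a family-wise error rate of 0.10".

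The same model specification is reused elsewhere:
- SAP 3.4.1.5 fits it separately in each subgroup: "The analysis for each subgroup will be performed if the subgroup has at least 20% of subjects in the ITT population".
- SAP 3.4.1.4 (fourth supplementary analysis) and 3.4.3.2 extend it to Week 24.
- SAP 3.4.2.3 applies it to the continuous secondary endpoints.

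**The concern.** Compound symmetry and first-order autoregressive structures, in their standard forms, have a single variance parameter. The Week 16 contrast is then judged against a variance pooled over all visits. Percent change from baseline is zero for everyone at baseline by construction, so its spread has to grow at some point, and it may still be growing after Week 1. If the Week 16 variance is above the pooled value, the Week 16 p-values are too small and the 90% confidence intervals too narrow. A fallback meant to rescue a fit would then undermine the error rate of that fit, and the analyst would choose it without a pre-specified order.

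**Working it through.** **Inputs from the documents.** N = 144 at 3:1:1:3, that is 54/18/18/54; SD 40 points; difference 35 points; two-sided alpha 0.10 (SAP 2.4 and 3.1). There are six post-baseline EASI visits to Week 16 (Weeks 1, 2, 4, 8, 12, 16) and eight to Week 24 (SAP Table 1). The documents give no SD for earlier visits, no between-visit correlation and no missing-data rate, so the SD patterns below are assumptions.

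**The plan's own figure.** Half of 54 gives 27 per arm in the responder subgroup. SE = 40 x sqrt(2/27) = 10.89, and 35/10.89 - 1.645 = 1.57, so power is 94%, consistent with the stated 90% or more. With 54 per arm, SE = 40 x sqrt(2/54) = 7.70 and power is 99.8%. The inputs are therefore read as the SAP intends.

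**Error rate under a pooled variance.** With complete data, the Week 16 estimate under either fallback is essentially the per-visit ANCOVA estimate. Its true SE is proportional to the Week 16 SD, while the model-based SE is proportional to the pooled SD. With ratio r = sqrt(mean of SD² over visits) / 40, the actual two-sided error is 2 x (1 - Phi(1.645 x r)).

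| Assumed SD by visit | Mean SD² | r | Actual error | 90% CI coverage |
|---|---|---|---|---|
| constant 40 | 1600 | 1.000 | 10% | 90% |
| 30, 32, 34, 36, 38, 40 | 7420/6 = 1236.7 | 0.879 | 14.8% | 85% |
| 20, 24, 28, 32, 36, 40 | 5680/6 = 946.7 | 0.769 | 20.6% | 79% |
| 45, 44, 43, 42, 41, 40 | 10855/6 = 1809.2 | 1.063 | 8.0% | 92% |

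Fitting the best autoregressive variance instead of the simple mean gave nearly the same values for these linear patterns.

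**Check by REML simulation** (54/18/18/54, six visits, 1200-1500 runs per setting, 0% or 25% missing completely at random):
- SD 20 to 40: 20% with complete data, 22-23% with 25% missing.
- SD 30 to 40, 25% missing: 15-17%.
- Constant SD: 9-10%, except about 12% when compound symmetry was fitted to autoregressive data with 25% missing.
- SD 45 to 40, 25% missing: 6-8%.

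A separate simulation using the visit-specific variance gave 9-10%. Over all assumed patterns examined, the error ranged from about 6% to 24%.

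**Week 24 models (eight visits, Week 16 contrast).** The same rise to 40 at Week 16 is assumed, followed by a plateau or a continued rise in equal steps.
- 20 to 40, plateau: (5680 + 3200)/8 = 1110, r = 0.833, error 17.1%.
- 20 to 40, continuing to 44 and 48: (5680 + 1936 + 2304)/8 = 1240, r = 0.880, error 14.8%.
- 30 to 40, plateau: (7420 + 3200)/8 = 1327.5, r = 0.911, error 13.4%.
- 30 to 40, continuing to 42 and 44: (7420 + 1764 + 1936)/8 = 1390, r = 0.932, error 12.5%.

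**Where a fallback could be needed.** An unstructured matrix has k(k+1)/2 parameters: 21 for six visits and 36 for eight. The primary fit has 21 for about 144 subjects. The smallest permitted subgroup has 0.20 x 144 = 28.8 to 0.20 x 152 = 30.4 subjects, so about 30 (roughly 11/4/4/11). That fit estimates 21 covariance parameters plus 24 treatment-by-visit means, 6 baseline slopes and 1 stratum term, with post-rescue data removed.

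**Would a sandwich standard error be enough?** At 54/18/18/54 it held the error at 10-12%. In an 11/4/4/11 subgroup an uncorrected sandwich gave about 14-19% even with constant SD, where the pooled-variance SE gave 10-11%.

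**The case against.** A reader might infer that using the fallback pushes the error rate to 15-20% in every case. The documents do not support that. The only SD they state is 40 points; nothing says how it changes over visits, and a constant or declining SD gives no inflation or a conservative test. That percent change starts from zero spread at baseline does not show how much growth remains after Week 1.

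A reader might also infer that the family-wise 0.10 of MCP-Mod is lost. That would need the fallback to be used in an MMRM that feeds MCP-Mod: the primary analysis and the first and third supplementary analyses. These are six-visit fits in close to the full sample, where the unstructured matrix should converge (a judgement, not a tested result). The Week 24 and subgroup MMRMs, where failure is more plausible, have no MCP-Mod step, and the IGA and EASI 75 analyses use logistic regression.

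Three further points stand. The SAP's wording offers the two structures as examples, so it does not exclude heterogeneous ones. The second supplementary analysis is an ANCOVA that does not pool variance over visits, although it relies on LOCF. The subgroup analyses assess consistency only, and about 30 subjects is the minimum size, not the typical one. The six-visit, SD 40 figures also do not carry over to endpoints on other scales, such as DLQI, 5-D itch and POEM, which have five visits to Week 16.

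These points limit the size and reach of the problem. They do not answer the core of it: the protocol deferred the detail to the SAP, and the only structures the SAP names carry an unverified equal-variance assumption.

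**Conclusion.** The point holds as a contingent weakness of low severity. It needs two conditions: the unstructured fit fails and an equal-variance structure replaces it, and the Week 16 variance exceeds the visit average. Under an assumed linear rise to 40 points, the nominal 10% error is then about 15% (from 30) or 21% (from 20) in six-visit models, and about 13-17% in the Week 24 models. The practical exposure is mainly in the separate subgroup fits and the Week 24 models. The percentages for small subgroups were not computed directly; the six-visit figures show the mechanism and the order of size. No inflation of the primary MCP-Mod test is claimed.

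**What to change.** Replace the fallback sentence in SAP 3.4.1.3 with a fixed order: heterogeneous Toeplitz, then heterogeneous first-order autoregressive, then heterogeneous compound symmetry, using the first that converges, with Kenward-Roger degrees of freedom. State that the rule applies to every MMRM that refers to this section. These structures keep a variance for each visit and are still much smaller than the unstructured matrix: for six visits, 6 + 5 = 11, 6 + 1 = 7 and 6 + 1 = 7 parameters against 21.

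Do not require an uncorrected sandwich standard error. If a robust standard error is used at all, specify a small-sample correction, and do not rely on it in the small subgroup fits.

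The cost is one sentence in the SAP and slightly wider intervals when the fallback is used.
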